## Study Endpoints

### Primary Endpoints

The bioequivalence of atropine sulfate administered SL versus administered IM as measured by the following PK parameters:

- Area under the analyte concentration versus time curve to infinity ( $AUC_{\infty}$ )
- Area under the analyte concentration versus time curve to time of last quantifiable data point ( $AUC_t$ )

### Secondary Endpoints

The relative bioavailability of atropine sulfate administered SL versus IM as measured by the following PK parameters:

- Area under the analyte concentration versus time curve to time 45, 60, 90, 120, 150, and 240 minutes ( $AUC_{45}$ ,  $AUC_{60}$ ,  $AUC_{90}$ ,  $AUC_{120}$ ,  $AUC_{150}$ , and  $AUC_{240}$ , respectively)
- Maximum measured plasma concentration ( $C_{max}$ )
- Time to  $C_{max}$  ( $t_{max}$ )
- Apparent terminal elimination half-life ( $t_{1/2}$ )
- Terminal elimination rate constant ( $\lambda_z$ )
- Volume of distribution ( $V_d/F$ )
- Total body clearance ( $CL/F$ )
- Absorption rate constant ( $K_a$ )

**Statistical methods:****Analysis Plan**

Statistical analyses will be performed using SAS® software Version 9.4 or later. Phoenix WinNonLin software Version 8.3 or later will be used to generate PK parameter estimates.

Descriptive statistics will be used to summarize participant characteristics and safety. These summaries will be presented overall and separately for each route of administration.

Pharmacokinetic parameter estimates will be summarized using descriptive statistics.

Bioavailability of SL administration of atropine sulfate relative to that of IM atropine sulfate will be assessed based on ratios of least-square means and their associated 90% confidence intervals (CIs) generated from linear mixed models including terms for dosing sequence, route, and period as fixed effects, and subject nested within dosing sequence as a random effect. Bioequivalence will be considered met if the 90% CI of the ratio for  $AUC_{\infty}$  and  $AUC_t$  lie within 80.00 to 125.00%.

Additional details of the statistical analyses, methods, and data conventions will be described in the Statistical Analysis Plan (SAP).

**Final Analyses**

A clinical study report will be written to include all PK and safety data collected throughout the study. For the final analysis, the study database will be monitored, cleaned, and locked per associated study plans. Further details will be specified in the SAP.

**Analysis Populations****PK Analysis Population**

The PK analysis population will include all participants who are randomized, receive at least 1 study drug dose, and have PK samples collected for that period. Each participant's data will be analyzed according to the corresponding route of administration for the applicable period. The PK analysis population will be used for all PK analyses.

**Per Protocol Population**

The per protocol population will include all participants who are randomized, receive atropine via both routes of administration according to their randomized dosing sequence, and have PK samples collected for both periods. In addition, participants with major protocol deviations may be excluded if it is determined that the deviations affect the integrity of PK data. Each participant's data will be analyzed according to the corresponding route of administration for the applicable period. Primary and secondary analyses will be repeated in the per protocol population if it differs from the PK analysis population.

**Safety Population**

The safety population will include all participants who are randomized and receive at least 1 study drug dose. Each participant's data will be analyzed according to the corresponding route of administration for the applicable period. The safety population will be used for all safety displays.

#### 4. GENERAL ANALYSES AND REPORTING CONVENTIONS

The following is a list of general analysis and reporting conventions to be applied for this study:

- Validation and quality control of analysis datasets, tables, listings, and figures will be performed as specified in the Statistical Validation and Quality Control Plan (SVP).
- Categorical variables will be summarized using counts (n) and percentages (%) and will be presented in the form n (%). Percentages will be rounded to one decimal place. If n=0, then no percent will be shown. To ensure completeness, all summaries for categorical and discrete variables will include all reportable categories, even if none of the participants had a response in a particular category.
- Numeric variables will be summarized using n, mean, standard deviation (SD), median, minimum (min), and maximum (max). For variables summarized using geometric means, coefficient of variation (CV%) of the geometric mean will be presented in lieu of SD. The min/max will be reported at the same level of significance as original data. The mean and median will be reported at one more significant digit than the precision of the data. SD and confidence intervals (CIs) will be reported at two more significant digits than the precision of the data. Precision may be modified based on clinical judgement.
- The median will be reported as the average of the two middle numbers if the dataset contains an even number of observations.
- Test statistics including t and z test statistics will be reported to two decimal places.
- P-values will be reported to 3 decimal places if greater than or equal to 0.001. If less than 0.001, the value will be reported as “<0.001”.
- In general, listings will be displayed by dosing sequence and participant and will be sorted in the order that columns are displayed, starting with the first column on the left.
- All analyses will be performed using the SAS System version 9.4 or higher. Figures will be programmed using SAS version 9.4 or higher or R version 3.4.1 or higher.
- Dates will be displayed as ddmmmyyyy (e.g., 26May2023).
- Calculations using dates will be performed as noted below.

*Visit 1 Date = Day 1*

Study day for dates after Visit 1/Day 1

*Study Day = Date – Visit 1 Date + 1*

Study day for dates prior to Visit 1/Day 1

*Study Day = Date – Visit 1 Date*

Total duration of days

Page 16 of 35

$$\text{Duration} = \text{End Date} - \text{Start Date} + 1$$

Note: no calculation will be needed for age as it will be pulled directly from the clinical database.

- For data collected at both screening and pre-dose on Visit 1/Day 1, the baseline data will be defined as the latest non-missing value collected. Otherwise, if data are collected at only one of Screening or Visit 1/Day 1, the collected value will be considered the baseline value for analyses.

If departures from these general conventions are present in the specific evaluation section of this SAP, then those conventions will take precedence over these general conventions.

## 5. ANALYSIS POPULATIONS

### 5.1. Consented Population

This includes all participants who give written informed consent. As such, this will include participants who are and are not randomized.

### 5.2. Not Randomized Population

This includes all participants who give written informed consent and are not randomized. Apart from reporting the reasons for not meeting inclusion/exclusion criteria or for not being randomized, those who are not randomized will not be included in any other analyses.

### 5.3. Randomized Population

The randomized population will include all participants who are randomized into the study, regardless of actually receiving a study drug dose. Each participant's data will be analyzed according to the randomized dosing sequence.

### 5.4. Safety Population

The safety population will include all participants who receive at least 1 study drug dose. Each participant's data will be analyzed according to the corresponding route of administration for the applicable period. The safety population will be used for all safety displays.

### 5.5. PK Analysis Population

The PK analysis population will include all participants who are randomized, receive at least 1 study drug dose, and have PK samples collected for that period. Each participant's data will be analyzed according to the corresponding route of administration for the applicable period. The PK analysis population will be used for all PK analyses.

### 5.6. Per Protocol Population

The per protocol population will include all participants who are randomized, receive atropine via both routes of administration according to their randomized dosing sequence, and have PK samples collected for both periods. In addition, participants with major protocol deviations may be excluded if it is determined that the deviations affect the integrity of PK data. Each participant's data will be analyzed according to the corresponding route of administration for the applicable period. Primary and secondary analyses will be repeated in the per protocol population if it differs from the PK analysis population.

## 6. VALIDATION AND QUALITY CONTROL PROCEDURES

Validation and quality control of datasets, summary tables, data listings, figures, and statistical analyses will be performed in accordance with the SVP.

## 7. STUDY PARTICIPANTS

### 7.1. Disposition of Participants

The disposition of all consented participants will be tabulated and listed. The numbers and percentages of participants consented, randomized, and terminating early, including reasons for early termination, will be presented. Percentages will be based on the number of participants at each level of summarization and within the specific study group, as applicable.

In addition, the reasons for ineligibility at screening/first study drug administration and ineligibility at the time of the second study drug administration will be listed separately.

Participants in each analysis population will be tabulated and listed for all randomized participants.

Visit completion will also be summarized for all randomized participants.

### 7.2. Demographic and Other Baseline Characteristics

A summary of descriptive statistics for baseline and demographic characteristics will be reported for the safety population. Characteristics to be summarized include age (years), race, ethnicity, sex, body weight at screening (kg), height (m), and BMI (kg/m^2). These characteristics will be recorded at the time of the Screening visit. A corresponding listing will also be created.

Body weight reported in pounds will be converted to kg via body weight in pounds divided by 2.2. Height reported in inches will be converted to cm via height in inches multiplied by 2.54. BMI will be calculated automatically within the electronic data capture (EDC) system.

### 7.3. Prior and Concomitant Medications

Medications will be coded according to the World Health Organization (WHO) Drug Dictionary (refer to the DSMP for the specific version). Medications reported on the case report form (CRF) will be categorized for analysis as prior, concomitant, or after study treatment by comparing the medication start and stop dates with the first and last dose of study medication dates. Prior medications will have both the medication start and stop dates prior to the first dose of study medication date. After medications will have both the medication start and stop dates after the last dose of study medication date. All other medications will be classified as concomitant, indicating that use of the medication overlapped with use of the study medication by at least one day.

The number and percentage of participants receiving prior and concomitant medications will be presented overall and by medication class. When reporting the number of participants receiving the medication, a participant will only be counted once if they ever received the medication within the medication class. Percentages will be based on the number of participants in the safety population.

Medication usage will be listed, including Anatomical Therapeutic Chemical (ATC) level 4 coding term, verbatim drug name, preferred drug name, start date, end date, dose (with unit), frequency, route, ongoing status and indication.

The following conventions will be used for imputing missing start dates.

- For start dates that are missing the day value with non-missing month and year:
  - The start day will be imputed as the first day of the non-missing start month.
- For start dates that are missing the day and month values with non-missing year:
  - If the start year is earlier than the year of Visit 1, the start month and day will be imputed as July 1.
  - If the start year is the same as the year of Visit 1, the start date will be set to the date of Visit 1.
  - If the start year is after the year of Visit 1, the start month and start day will be imputed as January 1.
- Completely missing start dates will be imputed as the date of Visit 1.

End dates will not be imputed.

#### 7.4. Medical History

Medical history items will be coded according to the Medical Dictionary for Regulatory Activities (MedDRA; refer to the DSMP for the specific version). Frequencies and percentages of participants with previous or current medical conditions or surgeries will be summarized by body system and dosing sequence for the safety population. A listing will also be created.

## 8. STUDY OPERATIONS

### 8.1. Protocol Deviations

Protocol deviations are defined in Section 15.3.1 of the protocol. All protocol deviations, including site level protocol deviations, will be listed by site with information such as type of deviation, severity of the deviation (major or non-major), date/day of occurrence, and the deviation details. Protocol deviations will be summarized in tabular format by type of deviation and dosing sequence.

As described in Section 5.5, protocol deviations will be used in the determining the composition of the per protocol population. Deviations resulting in exclusion from the per protocol population will be noted within the listing.

The severity of the deviation (major or non-major) will not be recorded in the CRFs by the sites. BARDA will review deviations to determine the severity of each, and this severity will be documented outside of the clinical database.

### 8.2. Blinding and Randomization

Eligible participants will be randomized at a 1:1 ratio to receive one of two treatment dosing sequences (A or B). Sequence A will receive sublingual (SL) atropine at Visit 1 followed by intramuscular (IM) atropine at Visit 2. Sequence B will receive IM atropine at Visit 1 followed by SL atropine at Visit 2. Randomization will be implemented per Section 10.7.1 of the protocol.

This is an open label study, and as such, the investigators, clinic personnel, and participants will not be blinded to the randomized treatment dosing sequence assignment. Rho, Alluent, and BARDA personnel will also not be blinded.

### 8.3. Measures of Treatment Compliance

Study drug administration adherence for each route of administration will be summarized and listed. Counts and percentages of participants receiving dose 1 and dose 2, separately, will be reported in tables; the denominator will be the number of participants within each group as randomized. For participants who receive both doses of study drug, the counts and percentages of subjects receiving both doses of study drug according to the correct dosing sequence will be summarized. For participants terminating study drug administration early, the reasons for terminating study drug early will also be presented.

Details will be listed for each administration, including date and time of administration, route received, whether full dosage was received, why full dose not received, and location of intramuscular administration/time held for sublingual administration.

## 9. EFFICACY EVALUATION

There are no protocol defined efficacy endpoints for this study. As such, this section is not applicable.

## 10. SAFETY EVALUATION

### 10.1. Overview of Safety Analysis Methods

All safety analyses will be carried out using the safety population defined in Section 5.3 unless otherwise noted.

Summary tables will present adverse events (AEs) summarized by route of administration and overall.

Listings will be prepared for all safety measurements. Unless noted otherwise in a specific section, all listings will be sorted in order of participant identifier (ID) and time of assessment (e.g., visit, time, and/or event).

### 10.2. Adverse Events

Any detrimental change in the participant's condition after signing informed consent and up to completion of the follow-up period after the last administration of study drug (i.e., through Follow-up [Day 15]) will be considered an AE and must be recorded.

All AEs will be classified by system organ class (SOC) and preferred term (PT), according to the Medical Dictionary for Regulatory Activities (MedDRA) version 27.0. The severity of AEs will be classified by the site investigator using the National Cancer Institute's (NCI's) Common Toxicity Criteria for Adverse Events (CTCAE) version 5.0. Relationship of AEs to study therapy (not related, unlikely related, possibly related, probably related, definitely related) will be assessed by the site investigator, based on their opinion. For summaries of study drug related AEs, the categories of "possibly related", "probably related", and "definitely related" will be considered study drug related. If the relationship is missing, it will be counted as "related" in summaries.

Treatment-emergent AEs are defined as AEs occurring after the participant received at least one dose of atropine. Treatment-emergent AEs will be identified as those with an onset date on or after the first dose of study medication.

If the start date of an AE is incomplete or missing, it will be assumed to have occurred on or after the first dose of investigational product, except if an incomplete date (e.g., month and year) clearly indicates that the event started prior to treatment.

The following conventions will be used for imputing missing start dates.

- For start dates that are missing the day value with non-missing month and year:
  - If the start year is the same as the year of first dose date, then do the following:
    - If the start month is the same as the month of first dose date, the start date will be imputed as the date of first dose date.

- If the start month is not the same as the month of first dose date, then the start date will be imputed as the first day of the non-missing start month.
  - If the start year is not the same as the year of first dose date, then the start day will be imputed as the first day of the start month.
- For start dates that are missing the day and month values with non-missing year:
  - If the start year is the same as the year of first dose date, the start date will be imputed as the date of first dose date.
  - If the start year is after the year of first dose date, the start month and start day will be imputed as January 1.
- Completely missing start dates will be imputed as the date of first dose date.

End dates will not be imputed.

If a participant experiences the same AE on multiple occasions, the event will be counted once for each occurrence when reporting the number of AEs. When reporting the number of participants experiencing the events, a participant will only be counted once if they experience at least one event within the particular SOC or PT. Percentages will be based on the number of participants in the safety population.

Additionally, when summarizing AEs by severity or relationship, the AE will be categorized according to the highest severity (or relationship) rating for that AE in that participant.

Each AE will be assigned to a route of administration based on the most recently received route of administration prior to the beginning of the adverse event. In order to standardize the follow-up time after each study route administration, summaries will include treatment-emergent AEs or serious AEs (SAEs) through 7 days after the last study route administration, inclusive of the study route administration day. In addition, treatment-emergent AEs and SAEs through study participation will be presented.

- An overall summary table of TEAEs throughout the study and through 7 days after last study drug dose will include:
  - Total number of TEAEs
  - Total number of TEAEs related to study drug
  - Total number of serious TEAEs
  - Total number of serious TEAEs related to study drug
  - Total number of severe (grade 3, 4, or 5) TEAEs
  - Total number of severe (grade 3, 4, or 5) TEAEs related to study drug
  - Total number of TEAEs leading to early termination of study drug

- Total number of TEAEs leading to early study withdrawal
- Total number of TEAEs leading to death
- TEAEs classified by MedDRA SOC and PT will be summarized for each route of administration and overall for all TEAEs throughout the study and through 7 days after last study drug dose, separately.
- TEAEs classified by MedDRA SOC, PT, and maximum severity will be summarized for each route of administration and overall for all TEAEs throughout the study and through 7 days after last study drug dose, separately.
- TEAEs classified by MedDRA SOC, PT, and strongest relationship will be summarized for each route of administration and overall for all TEAEs through 7 days after last study drug dose.
- TEAEs classified by MedDRA SOC and PT will be summarized for each route of administration and overall for all serious TEAEs throughout the study and through 7 days after last study drug dose, separately.
- TEAEs classified by MedDRA SOC and PT will be summarized for all TEAEs leading to early termination of study drug, study withdrawal, and death, separately.

Corresponding listings will be created for the above-mentioned tables.

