11. ASSESSMENT OF PHARMACOKINETICS

Blood samples will be collected from each participant for PK assessments by a designated, qualified individual from the study research team. At Visit 1 (Day 1) and Visit 2 (Day 8), an indwelling venous catheter will be placed before dose administration for blood sample collection for serial determinations at the following times: 0 (pre-dose) and at 13 time points post-dose at 5, 10, 15, 20, 30, 45, 60, and 90 minutes, and 2, 2.5, 4, 6, and 8 hours. Ten (10) mL of whole blood will be collected into a sterile vacutainer containing ethylenediaminetetraacetic acid (EDTA) as a preservative for each sampling. Plasma will be stored frozen until analysis.

Pharmacokinetic samples will be analyzed by a bioanalytical facility approved by BARDA.

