12.3.2. Recording Adverse Events

Throughout the study, the investigator will record AEs on the eCRF. SAEs must be reported to Rho pharmacovigilance personnel within 1 business day of the site's awareness of the event. For the purposes of this study, any detrimental change in the participant's condition after signing informed consent and up to completion of the follow-up period after the last administration of study drug (i.e., through Follow-up [Day 15]) will be considered an AE and must be recorded. Treatment-emergent AEs are defined as AEs occurring after the participant receives at least one dose of atropine. AEs will be followed per the below criteria:

- AEs judged at least possibly related to study drug will be followed to resolution (with or without sequelae) or until considered stable by the investigator (in consultation with the medical monitor in situations of uncertainty).
- AEs judged unrelated to study drug will be followed to resolution (with or without sequelae) or, if not resolving, until considered stable by the investigator (in consultation with the medical monitor in situations of uncertainty), or until the end of the participant's study participation, whichever comes first.

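### The SAP defines treatment-emergent AEs by sequence but flags them by calendar date, so an event that starts before dosing on Day 1 is counted as treatment-emergent with no route to assign it to.

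*SAP*

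**What the plan says.** SAP section 10.2 gives the definition first: "Treatment-emergent AEs are defined as AEs occurring after the participant received at least one dose of atropine". Protocol section 12.3.2 gives the same definition and adds no date rule. The next SAP sentence turns the definition into a rule for the data: "Treatment-emergent AEs will be identified as those with an onset date on or after the first dose of study medication".

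Route is assigned by a separate rule later in the same section. Each AE is credited "based on the most recently received route of administration prior to the beginning of the adverse event".

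Four other provisions bear on the point:

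- SAP section 10.2 counts as an AE any detrimental change "after signing informed consent and up to completion of the follow-up period after the last administration of study drug", so recording starts before any drug is given.
- Protocol section 11 states that at Visits 1 and 2 "an indwelling venous catheter will be placed before dose administration for blood sample collection".
- The Schedule of Assessments (Protocol Appendix 2) marks AE collection separately for the Day 1 and Day 8 pre-dose and dosing columns.
- SAP section 8.3 lists each administration, "including date and time of administration". The AE conventions in SAP section 10.2 speak of start dates only. They mention neither an AE onset time nor a before/after-dose indicator.

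**The concern.** The two adjacent sentences in SAP section 10.2 are meant to describe the same set of events, but they differ on the first dosing day. An event that begins on Day 1 before the dose, for example at catheter placement, is outside the definition and inside the date rule. A programmer will implement the date rule. SAP section 2 gives the SAP precedence over the protocol where they differ. SAP section 13 lists only a change to the safety population, so the departure looks unintended.

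Such an event then meets a route rule that has nothing to work with, because no route has yet been received. It would enter the overall column and no route column, and the event counts by route would not add up to the total.

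A related gap is that the SAP has no stated order for an AE whose onset date equals a dosing date. The main AE tables are presented by route, so the boundary at each dose decides which column an event falls in.

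**Working it through.** There is no stated figure to reproduce. The check applies the SAP's definition, its date rule and its route rule to each possible onset. Visit 1 is Day 1. Visit 2 is 7 ± 1 days later, so it falls on Day 7 to Day 9 and is nominally Day 8. The last two columns show what happens if the route rule were run on dates alone, under each of the two possible tie conventions.

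| Onset | TEAE by definition | TEAE by date rule | Route by sequence, as worded | Dates only: same day counts as prior | Dates only: strictly earlier date |
|---|---|---|---|---|---|
| Day 1, pre-dose | No | **Yes** | None exists | Period 1 (wrong) | None |
| Day 1, post-dose | Yes | Yes | Period 1 | Period 1 | None (wrong) |
| Between dosing days | Yes | Yes | Period 1 | Period 1 | Period 1 |
| Day 8, pre-dose | Yes | Yes | Period 1 | Period 2 (wrong) | Period 1 |
| Day 8, post-dose | Yes | Yes | Period 2 | Period 2 | Period 1 (wrong) |

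1. **Treatment-emergent flag.** The definition and the date rule disagree in one row only, Day 1 pre-dose. In every other row the participant has already had a dose, so the flag is right.
2. **Route as worded.** The rule gives the correct answer in every row where a route exists. It gives none for Day 1 pre-dose, which is the row the date rule wrongly admits.
3. **Route on dates alone.** Neither tie convention is right throughout. Counting the same day as prior misplaces the pre-dose events on both dosing days. Requiring an earlier date misplaces the post-dose events on both. The ordering therefore needs a time or a before/after-dose indicator, and the SAP names neither for AEs.
4. **Imputed dates.** SAP section 10.2 sets a wholly missing AE start date, and some partial ones, to the date of first dose. These dates carry no time, so they add further same-day ties on Day 1. The SAP settles their treatment-emergent status by assumption, but it gives no convention for ordering them against the dose when route is assigned.

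**Scale.** The documents give no rate for pre-dose events on dosing days, so the number affected cannot be computed. As a scale only, with about 46 participants in the safety population, each participant wrongly counted moves an overall percentage by 1/46 = 2.2 percentage points.

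**The case against.** The best case for the plan has four parts.

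**The intent is clear.** Protocol and SAP share one definition, and the date sentence may be only shorthand for it. This is fair as to intent. But the date sentence is the one that says how events will be identified, and on complete dates it gives the wrong answer for Day 1 pre-dose events.

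**The data to separate events may already exist.** The eCRF, the Data Safety Monitoring Plan and the table shells are separate documents. SAP section 10.1 mentions time generically as a sort key for listings, and the schedule has distinct pre-dose and dosing columns. This stands. The documents do not show that AE onset time is missing; they show only that the SAP does not say it will be used.

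**Over-inclusion is conservative.** The SAP also assumes that AEs with missing dates followed the first dose, and it counts a missing relationship as related. Those conventions deal with missing information, however. Here the date is complete, and the sequence may be known.

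**A reader might infer that Day 8 events cannot be placed under the right route.** The documents do not support this. The sentence on treatment emergence does not govern route. The route rule is sequential and places both pre-dose and post-dose Day 8 events correctly once their order is known. Nor is a Day 8 pre-dose event wrongly flagged: anyone dosed on Day 1 has already received a dose, so the event is treatment-emergent by definition.

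**Conclusion.** The point holds in a limited form. As written, the identification rule in SAP section 10.2 contradicts the definition before it. It counts Day 1 pre-dose events as treatment-emergent, and the assignment rule has no route for them. Separately, the SAP does not state how an AE dated to a dosing day is ordered against the dose. On Day 8 that becomes a real problem only if the programming uses dates alone, which the documents neither confirm nor exclude.

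It is tempting to go further and say that a dates-only reading would erase or reverse a difference between routes. The documents do not support that. They give no AE incidence by route for this comparison. A strictly-earlier-date reading would also leave every Day 1 post-dose event without a route, which is not a plausible reading to attribute to the SAP.

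The size cannot be computed, and it is nil if no AE begins before dosing on Day 1 and onset order is known on both dosing days. Only the descriptive safety tables are affected; the bioequivalence conclusion is not. This is a minor point, worth correcting before database lock because it is so easily corrected.

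**What to change.** Replace the date rule in SAP section 10.2 with one rule that serves both purposes: treatment emergence and route are determined by AE onset date and time relative to the recorded dose date and time. Then add:

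- Where onset time is not available and the onset date is a dosing day, use the schedule's collection point. An AE recorded at the pre-dose assessment precedes that day's dose; one recorded in the dosing column follows it.
- State a fallback for events whose order is still unknown. These include imputed start dates and dosing-day events first reported at a later contact. One option is to treat them as following that day's dose, which fits the SAP's existing assumption for missing start dates.
- Report Day 1 pre-dose events in listings, outside the treatment-emergent tables.

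The cost is a sentence or two in the SAP and a matching line in the programming specification. Dose time is already listed, and the pre-dose and dosing collection points already exist. First check whether the eCRF captures AE onset time or a before/after-dose indicator; if it does, no data collection changes. If it does not, the collection-point rule still works without a new field.
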